12 MEASUREMENT OF EFFECT

12.1 ANTITUMOR EFFECT – SOLID TUMORS

For the purposes of this study, patients should be re-evaluated for response every 6 weeks for patients on treatment < 1 year; every 12 weeks for patients on treatment \geq 1 year. In addition to a baseline scan, confirmatory scans should also be obtained 4 weeks following initial documentation of objective response.

Response and progression will be evaluated in this study using the new international criteria proposed by the revised Response Evaluation Criteria in Solid Tumors (RECIST) guideline (version 1.1)¹⁴⁵. Changes in the largest diameter (unidimensional measurement) of the tumor lesions and the shortest diameter in the case of malignant lymph nodes are used in the RECIST criteria.

12.1.1 Definitions

Evaluable for toxicity: All patients will be evaluable for toxicity from the time of their first treatment with sunitinib.

Evaluable for objective response: Only those patients who have received at least one cycle of therapy, and have had their disease re-evaluated will be considered evaluable for response. These patients will have their response classified according to the definitions stated below. (Note: Patients who exhibit objective disease progression prior to the end of cycle 1 will also be considered evaluable.)

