For thymic carcinomas, the study will try to rule out a 5% objective response rate ($p_0=0.05$) and target a modest response rate of 25% ($p_1=0.25$). The study will initially enroll 9 evaluable patients with thymic carcinoma; if 0 of the 9 patients demonstrate a partial response then no further patients will be accrued. If 1 or more of the first 9 patients have a response, then accrual would continue until a total of 24 evaluable patients have been treated. A temporary pause in the accrual to the trial may be necessary to ensure that enrollment to the second stage is warranted. If there are 1 to 2 patients with a response in the total of 24 evaluable patients, then this would be an uninterestingly low rate, while if there were 3 or more patients of the 24 who have a response, this would be sufficiently interesting to warrant further study of this agent in later trials. Under the null hypothesis (5% response rate), the probability of early termination in this cohort is 63%. For thymomas, the study will try to rule out a 10% objective response rate ($p_0=0.10$) and target a modest response rate of 30% ($p_1=0.30$). The study will initially enroll 16 evaluable patients with thymoma; if 0 to 1 of the 16 patients demonstrate a partial response then no further patients will be accrued. If 2 or more of the first 16 patients have a response, then accrual would continue until a total of 25 evaluable patients have been treated. A temporary pause in the accrual to the trial may be necessary to ensure that enrollment to the second stage is warranted. If there are 2 to 4 patients with a response in the total of 25 evaluable patients, then this would be an uninterestingly low rate, while if there were 5 or more patients of the 25 who have a response, this would be sufficiently interesting to warrant further study of this agent in later trials. Under the null hypothesis (10% response rate), the probability of early termination in this cohort is 51%.

Group 2

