17.2 SAMPLE SIZE/ACCRUAL RATE

12-C-0118 used a Simon 2-stage design with an accrual ceiling of 52 (Group 1) based on the assumption that the individual cohorts for thymoma and thymic carcinoma would proceed to the second stage with accrual ceilings of 25 and 24 evaluable patients respectively (plus an additional 3 patients to allow for a small number of inevaluable patients.) However, the results from the study demonstrated only 1 PR in the thymoma cohort among the first 16 evaluable patients, and hence accrual was halted at 16 patients as previously specified and did not proceed to the accrual ceiling of 25 patients for this cohort (2 or more responses needed to be observed to proceed to 25 patients.) However, in the thymic carcinoma cohort more than 1 PR was observed in the first 9 evaluable patients. Hence, accrual proceeded to the second stage with an accrual ceiling of 24 patients in this cohort. The total accrual in study 12-C-0118 was therefore $16+25=41$ patients. Therefore, a total of 11 slots remained unfilled in the original study due to the inability of the thymoma cohort to proceed to the second-stage of accrual.

In Amendment E, (version date 05/12/14), we provide a justification to evaluate sunitinib in patients with thymic carcinoma while discontinuing evaluation of this drug in patients with thymoma. Further, we would like to evaluate sunitinib in thymic carcinoma using a modified dosing schedule in an additional 15 patients (Group 2). Hence, we would like to utilize the 9 unfilled thymoma slots from the original study, add 6 new slots (to obtain 15 slots for the new thymic carcinoma cohort, Group 2) and retain 2 slots for inevaluable patients for an accrual ceiling of $52+6=58$ patients.

It is anticipated that approximately 3 patients per month overall may enroll on this trial. Group 1 accrual was completed in less than two years. Thus, Group 2 accrual should be completed with approximately one additional year, thereby completing overall trial accrual in a total of three years. Progression free and overall survival will also be determined for each group separately, using Kaplan-Meier curves, and reported as a secondary endpoint.

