17.5.2 Evaluation of response

All patients included in the study must be assessed for response to treatment, even if there are major protocol treatment deviations or if they are ineligible. Each patient will be assigned one of the following categories: 1) complete response, 2) partial response, 3) stable disease, 4) progressive disease, 5) early death from malignant disease, 6) early death from toxicity, 7) early death because of other cause, or 9) unknown (not assessable, insufficient data). [Note: By arbitrary convention, category 9 usually designates the “unknown” status of any type of data in a clinical database.]

All of the patients who met the eligibility criteria (with the possible exception of those who received no study medication) should be included in the main analysis of the response rate. Patients in response categories 4-9 should be considered to have a treatment failure (disease progression). Thus, an incorrect treatment schedule or drug administration does not result in exclusion from the analysis of the response rate. Precise definitions for categories 4-9 will be protocol specific.

All conclusions should be based on all eligible patients. Subanalyses may then be performed on the basis of a subset of patients, excluding those for whom major protocol deviations have been identified (*e.g.*, early death due to other reasons, early discontinuation of treatment, major protocol deviations, etc.). However, these subanalyses may not serve as the basis for drawing conclusions concerning treatment efficacy, and the reasons for excluding patients from the analysis should be clearly reported. The 95% confidence intervals should also be provided.

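### The plan gives two denominators for the response rate, evaluable patients (12.1.1, 17.1) and all eligible patients (17.5.2), and never says how they fit together

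*Combined protocol and SAP*

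**What the plan says.** All references are to the combined protocol and SAP.

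- **12.1.1 Definitions:** "Only those patients who have received at least one cycle of therapy, and have had their disease re-evaluated will be considered evaluable for response". A note adds patients whose disease objectively progresses before cycle 1 ends.
- **17.1, Group 1:** both two-stage designs count evaluable patients. For thymic carcinoma, "accrual would continue until a total of 24 evaluable patients have been treated", and the agent merits further study "if there were 3 or more patients of the 24 who have a response".
- **17.2:** the Group 1 ceiling is 25 and 24 evaluable patients, "plus an additional 3 patients to allow for a small number of inevaluable patients". When Group 2 was added, the plan was to "retain 2 slots for inevaluable patients".
- **17.5.2:** every patient who met the eligibility criteria, possibly excepting those never dosed, belongs in the main response-rate analysis. "Patients in response categories 4-9 should be considered to have a treatment failure (disease progression"), and these categories include early death and not assessable. "All conclusions should be based on all eligible patients". Subanalyses that leave patients out, for example for stopping early, may not support efficacy conclusions.

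For Group 2, 17.1 speaks only of 15 patients. Evaluability reaches that group through 12.1.1 and the two retained slots.

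**The concern.** Take a treated, eligible patient who stops for toxicity during cycle 1 with no documented progression. Under 12.1.1 this patient is outside the response denominator. Under 17.5.2 the patient is inside it and counts as a failure. Both rules cannot be followed, and no section says which one gives the primary response rate.

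The evaluable-only rate is biased upward, because the patients it removes are treated non-responders. The bias is limited: early objective progressors stay in, so it comes only from patients who stop or die without documented progression. In a small single-arm trial whose primary endpoint is the response rate, an unsettled denominator leaves a choice that could be made with the results in view.

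A secondary point concerns the one-cycle threshold. A cycle is 6 weeks in Group 1 and 3 weeks in Group 2 (Précis, section 5.1.1), so the evaluable sets of the two groups are not like for like. Yet 17.1 makes similarity to the Group 1 response rate the aim of Group 2.

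**Working it through.** **1. The plan's own design figures reproduce.** Exact two-stage binomial, in evaluable patients (17.1):

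- Thymic carcinoma (stop at 0/9, positive at 3 or more of 24; p0 = 0.05, p1 = 0.25). P(early stop | p0) = 0.95^9 = 0.630 (stated 63%). P(positive) = Σ over x = 1 to 9 of P(X1 = x) × P(X2 ≥ 3 − x), with X1 ~ Bin(9, p) and X2 ~ Bin(15, p). This gives alpha 0.093 and power 0.903, against limits of 0.10 and 0.90.
- Thymoma (stop at 0 or 1 of 16, positive at 5 or more of 25; p0 = 0.10, p1 = 0.30): early stop 0.515 (stated 51%), alpha 0.095, power 0.903.
- Group 2 precision: 1.645 × √(0.26 × 0.74 / 15) = 18.6 points, as stated for the 90% interval.

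The sample-size arithmetic is therefore not at fault.

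**2. The denominator in the Group 1 results.** Table 3B and Table 5 give 5 partial responses among 22 thymic carcinoma patients. Table 5 adds 15 with stable disease. Section 17.2 gives total accrual as 16 + 25 = 41, so 25 − 22 = 3 thymic carcinoma patients are not in the tables. Section 2.3.2 uses 41 as the denominator for dose reductions, which suggests that all 41 were treated but does not establish it. Intervals are exact (Clopper-Pearson) 95%.

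| Denominator | Response rate | 95% interval | Disease control |
|---|---|---|---|
| 22 (as tabulated) | 5/22 = 22.7% | 7.8 to 45.4 | 20/22 = 91% |
| 25 (all accrued; the other 3 assumed eligible, treated, non-responding and without disease control) | 5/25 = 20.0% | 6.8 to 40.7 | 20/25 = 80% |

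The 23% and 91% quoted in sections 2.1 and 2.3.2 are thus the 22-patient figures. The response-rate difference is 22.7 − 20.0 = 2.7 points.

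**3. Group 2.** Suppose 4 responders, 15 evaluable patients, and 0, 1 or 2 inevaluable patients in the retained slots who count as failures:

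- 4/15 = 26.7% (7.8 to 55.1)
- 4/16 = 25.0% (7.3 to 52.4)
- 4/17 = 23.5% (6.8 to 49.9)

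The largest shift is 26.7 − 23.5 ≈ 3.1 points before rounding.

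**4. The benchmark.** Section 17.1 puts the earlier rate at approximately 26% without a numerator or denominator. With the 5 responders reported, 22 patients give 22.7% and 25 give 20.0%, and neither is 26%. The population behind the benchmark is therefore unknown.

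**5. Completed decisions.** Five thymic carcinoma responses exceed the 3 required. Thymoma stopped at 1/16, as specified. Neither outcome depends on whether inevaluable patients are added as failures.

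**6. Why the two-stage rule should stay on evaluable patients.** If the same cut-offs were applied to 24 eligible patients of whom an assumed 10% were inevaluable failures, the response probability under p1 would be 0.25 × 0.90 = 0.225, and power would fall from 0.903 to 0.862.

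**7. The one-cycle threshold.** Read as calendar time, it is 6 weeks against 3. Read as dosing, it is 4 weeks against 2, because weeks 5 and 6 are drug-free in Group 1 and week 3 is in Group 2. Evaluability also needs a re-evaluation, and scheduled scans fall every 6 weeks in both groups (12.1). The difference therefore bites mainly for a patient who stops before the first scheduled scan without progression but is imaged on stopping. Such a patient may be evaluable in Group 2 and not in Group 1. The documents give no share of such patients, so no size is put on it.

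**The case against.** The best reply is that 17.5.2 already settles the matter. It names the main analysis, chooses the conservative denominator, bars exclusion subanalyses as a basis for efficacy conclusions, and asks for reasons for exclusion and 95% intervals. A sensible reader would use evaluable patients for the two-stage counts and eligible patients for the reported rate. The shifts are also small beside the stated ±18.6 points, in a pilot group with no decision rule.

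Much of this stands. The plan does not license an evaluable-only primary rate, and a reader who infers that it does would be wrong. But the sensible division of labour is not written down. The word Only in 12.1.1 and the sweep of "All conclusions should be based on all eligible patients" both cut against it, because the rule of 3 or more in 24 evaluable patients is itself an efficacy conclusion. The tabulated Group 1 rate also does not use the 25 patients accrued.

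Four stronger readings are tempting, and the documents do not support them:

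- **Type I error exceeds 10%.** This needs the 5% null rate to refer to all treated patients. Section 17.1 states the design in evaluable patients, where alpha is 0.093.
- **The undefined categories leave the response rate open.** Section 17.5.2 does say "Precise definitions for categories 4-9 will be protocol specific", but every patient in them is a failure, so their definitions move neither numerator nor denominator.
- **The three missing patients were dropped as inevaluable.** The documents do not say so, and a data cut-off is equally possible.
- **A Group 1 patient stopping between weeks 3 and 6 is certainly inevaluable.** That holds only if a cycle means six calendar weeks. Someone who has taken all 28 doses has arguably received it.

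**Conclusion.** The contradiction is in the text and confidence in it is high. Section 17.5.2 is worded as governing the reported rate, yet it conflicts with 12.1.1 and with the 17.1 conclusion on 24 evaluable patients, and no section reconciles them.

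The size is modest: about 2.7 points for Group 1 thymic carcinoma if the three untabulated patients were eligible, treated non-responders, and up to 3.1 points for Group 2 in the four-responder illustration with both spare slots used. What is affected is the reported response rate, its interval and the informal comparison of Group 2 with Group 1. Group 2 has no formal rule to disturb. The unequal one-cycle threshold is secondary: it matters only where evaluable sets are compared and has no effect on the 17.5.2 analysis. Severity lies between minor and should-fix.

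**What to change.** - In 12.1.1 and 17.1, state that the primary reported response rate for both groups follows 17.5.2: all eligible patients who received at least one dose, with no documented response counted as non-response.
- In 17.5.2, write in an explicit exception: the Group 1 stage counts, go/no-go rule and error rates apply to patients evaluable under 12.1.1. Any other use of the evaluable set is a subanalysis. Without this exception the amended text would again assign Group 1 conclusions to two populations.
- Compare Group 2 with its Group 1 benchmark on the same denominator of all eligible treated patients, and give the benchmark's numerator and denominator in place of the bare 26%.

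The cost is wording only. No new data are needed, and accrual, spare slots and completed decisions stay as they are. The one downside is that the reported response rate may come out slightly lower.

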12.1.2 Disease Parameters

Measurable disease: Measurable lesions are defined as those that can be accurately measured in at least one dimension (longest diameter to be recorded) as:

- By chest x-ray: ≥ 20 mm;
- By CT scan:
 - Scan slice thickness 5mm or under: as ≥ 10 mm
 - Scan slice thickness > 5 mm: double the slice thickness
 - With calipers on clinical exam ≥ 10 mm

All tumor measurements must be recorded in millimeters (or decimal fractions of centimeters).

Note: Tumor lesions that are situated in a previously irradiated area might or might not be considered measurable.

Malignant lymph nodes: To be considered pathologically enlarged and measurable, a lymph node must be ≥ 15 mm in short axis when assessed by CT scan (CT scan slice thickness recommended to be no greater than 5 mm). At baseline and in follow-up, only the short axis will be measured and followed.

Non-measurable disease: All other lesions (or sites of disease), including small lesions (longest diameter <10 mm or pathological lymph nodes with ≥ 10 to <15 mm short axis), are considered non-measurable disease. Bone lesions, leptomeningeal disease, ascites, pleural/pericardial effusions, lymphangitis cutis/pulmonitis, inflammatory breast disease, and abdominal masses (not followed by CT or MRI), are considered as non-measurable.

Note: Cystic lesions that meet the criteria for radiographically defined simple cysts should not be considered as malignant lesions (neither measurable nor non-measurable) since they are, by definition, simple cysts.

‘Cystic lesions’ thought to represent cystic metastases can be considered as measurable lesions, if they meet the definition of measurability described above. However, if non-cystic lesions are present in the same patient, these are preferred for selection as target lesions.

Target lesions: All measurable lesions up to a maximum of 2 lesions per organ and 5 lesions in total, representative of all involved organs, should be identified as **target lesions** and recorded and measured at baseline. Target lesions should be selected on the basis of their size (lesions with the longest diameter), be representative of all involved organs, but in addition should be those that lend themselves to reproducible repeated measurements. It may be the case that, on occasion, the largest lesion does not lend itself to reproducible measurement in which circumstance the next largest lesion which can be measured reproducibly should be selected. A sum of the diameters (longest for non-nodal lesions, short axis for nodal lesions) for all target lesions will be calculated and reported as the baseline sum diameters. If lymph nodes are to be included in the sum, then only the short axis is added into the sum. The baseline sum diameters will be used as reference to further characterize any objective tumor regression in the measurable dimension of the disease.

Non-target lesions: All other lesions (or sites of disease) including any measurable lesions over and above the 5 target lesions should be identified as **non-target lesions** and should also be recorded at baseline. Measurements of these lesions are not required, but the presence, absence, or in rare cases unequivocal progression of each should be noted throughout follow-up.

12.1.3 Methods for Evaluation of Measurable Disease

All measurements should be taken and recorded in metric notation using a ruler or calipers. All baseline evaluations should be performed as closely as possible to the beginning of treatment and never more than 4 weeks before the beginning of the treatment.

The same method of assessment and the same technique should be used to characterize each identified and reported lesion at baseline and during follow-up. Imaging-based evaluation is preferred to evaluation by clinical examination unless the lesion(s) being followed cannot be imaged but are assessable by clinical exam.

Clinical lesions: Clinical lesions will only be considered measurable when they are superficial (e.g., skin nodules and palpable lymph nodes) and ≥ 10 mm diameter as assessed using calipers (e.g., skin nodules). In the case of skin lesions, documentation by color photography, including a

ruler to estimate the size of the lesion, is recommended.

Chest x-ray: Lesions on chest x-ray are acceptable as measurable lesions when they are clearly defined and surrounded by aerated lung. However, CT is preferable.

Conventional CT and MRI: This guideline has defined measurability of lesions on CT scan based on the assumption that CT slice thickness is 5 mm or less. If CT scans have slice thickness greater than 5 mm, the minimum size for a measurable lesion should be twice the slice thickness. MRI is also acceptable in certain situations (*e.g.* for body scans).

Use of MRI remains a complex issue. MRI has excellent contrast, spatial, and temporal resolution; however, there are many image acquisition variables involved in MRI, which greatly impact image quality, lesion conspicuity, and measurement. Furthermore, the availability of MRI is variable globally. As with CT, if an MRI is performed, the technical specifications of the scanning sequences used should be optimized for the evaluation of the type and site of disease. Furthermore, as with CT, the modality used at follow-up should be the same as was used at baseline and the lesions should be measured/assessed on the same pulse sequence. It is beyond the scope of the RECIST guidelines to prescribe specific MRI pulse sequence parameters for all scanners, body parts, and diseases. Ideally, the same type of scanner should be used and the image acquisition protocol should be followed as closely as possible to prior scans. Body scans should be performed with breath-hold scanning techniques, if possible.

Ultrasound: Ultrasound is not useful in assessment of lesion size and should not be used as a method of measurement. Ultrasound examinations cannot be reproduced in their entirety for independent review at a later date and, because they are operator dependent, it cannot be guaranteed that the same technique and measurements will be taken from one assessment to the next. If new lesions are identified by ultrasound in the course of the study, confirmation by CT or MRI is advised. If there is concern about radiation exposure at CT, MRI may be used instead of CT in selected instances.

Endoscopy, Laparoscopy: The utilization of these techniques for objective tumor evaluation is not advised. However, such techniques may be useful to confirm complete pathological response when biopsies are obtained or to determine relapse in trials where recurrence following complete response (CR) or surgical resection is an endpoint.

Cytology, Histology: These techniques can be used to differentiate between partial responses (PR) and complete responses (CR) in rare cases (*e.g.*, residual lesions in tumor types, such as germ cell tumors, where known residual benign tumors can remain).

The cytological confirmation of the neoplastic origin of any effusion that appears or worsens during treatment when the measurable tumor has met criteria for response or stable disease is mandatory to differentiate between response or stable disease (an effusion may be a side effect of the treatment) and progressive disease.

